8.3.1. Time Period and Frequency for Collecting AE and SAE Information

All AEs will be collected from the signing of the Informed Consent Form (ICF) until subject withdrawal or the scheduled exit visit. (Note: Although AEs will be monitored for and collected prior to IP administration, the statistical data analysis will determine and summarize treatment-emergent AEs, *i.e.*, those AEs that began or worsened in severity after the first IP administration.)

All SAEs will be recorded and reported to the sponsor or designee immediately and under no circumstance should this exceed 24 hours, as indicated in Section 10.3. The investigator will submit any updated SAE data to the sponsor within 24 hours of it being available.

Investigators are not obligated to actively seek AE or SAE after conclusion of the study participation. However, if the investigator learns of any SAE, including a death, at any time after

a participant has been discharged from the study, and he/she considers the event to be reasonably related to the study intervention or study participation, the investigator must promptly notify the sponsor.

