10.3.1. Definition of AE

AE Definition

- An AE is any untoward medical occurrence in a patient or clinical study participant, temporally associated with the use of study intervention, whether or not considered related to the study intervention.
- NOTE: An AE can therefore be any unfavorable and unintended sign (including an abnormal laboratory finding), symptom, or disease (new or exacerbated) temporally associated with the use of study intervention.

Events Meeting the AE Definition

- Any abnormal laboratory test results (hematology, clinical chemistry, or urinalysis) or other safety assessments (*e.g.*, ECG, radiological scans, vital signs measurements), including those that worsen from baseline, considered clinically significant in the medical and scientific judgment of the investigator (*i.e.*, not related to progression of underlying disease).
- Exacerbation of a chronic or intermittent pre-existing condition including either an increase in frequency and/or intensity of the condition.
- New conditions detected or diagnosed after study intervention administration even though it may have been present before the start of the study.
- Signs, symptoms, or the clinical sequelae of a suspected drug-drug interaction.
- Signs, symptoms, or the clinical sequelae of a suspected overdose of either study intervention or a concomitant medication. Overdose per se will not be reported as an AE/SAE unless it is an intentional overdose taken with possible suicidal/self-harming intent. Such overdoses should be reported regardless of sequelae.
- The signs, symptoms, and/or clinical sequelae resulting from lack of efficacy will be reported as AE or SAE if they fulfil the definition of an AE or SAE. Also, "lack of efficacy" or "failure of expected pharmacological action" also constitutes an AE or SAE.

Events **NOT** Meeting the AE Definition

- Any clinically significant abnormal laboratory findings or other abnormal safety assessments which are associated with the underlying disease, unless judged by the investigator to be more severe than expected for the participant's condition.
- The disease/disorder being studied or expected progression, signs, or symptoms of the disease/disorder being studied, unless more severe than expected for the participant's condition.
- Medical or surgical procedure (*e.g.*, endoscopy, appendectomy): the condition that leads to the procedure is the AE.

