- The investigator will also consult the Investigator's Brochure (IB) and/or Product Information, for marketed products, in his/her assessment.
- For each AE/SAE, the investigator **must** document in the medical notes that he/she has reviewed the AE/SAE and has provided an assessment of causality.
- There may be situations in which an SAE has occurred, and the investigator has minimal information to include in the initial report to Santen. However, it is very important that the investigator always make an assessment of causality for every event before the initial transmission of the SAE data to Santen.
- The investigator may change his/her opinion of causality in light of follow-up information and send a SAE follow-up report with the updated causality assessment.
- The causality assessment is one of the criteria used when determining regulatory reporting requirements.

AE and SAE Recording

Follow-up of AEs and SAEs

- The investigator is obligated to perform or arrange for the conduct of supplemental measurements and/or evaluations as medically indicated or as requested by Santen to elucidate the nature and/or causality of the AE or SAE as fully as possible. This may include additional laboratory tests or investigations, histopathological examinations, or consultation with other health care professionals.
- If a participant dies during participation in the study or during a recognized follow-up period, the investigator will provide Santen with a copy of any post-mortem findings including histopathology
- New or updated information will be recorded in the originally completed CRF.
- The investigator will submit any updated SAE data to Santen within 24 hours of receipt of the information.

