#### 2.2.4. Exploratory Endpoints

# **3. STUDY DESIGN**

### **3.1.** General Study Design

This is a Phase IIa, randomized, double-masked, placebo-controlled, parallel-group study assessing the efficacy and safety of STN1013600 ophthalmic solution (0.1% and 0.3%) in subjects with Presbyopia.

Subjects with Presbyopia who meet all eligibility criteria at Visit 1 (Screening) will be randomized at Visit 2 (Baseline) to receive treatment for 2 months.

Approximately 75 subjects who meet all eligibility criteria at Visit 1 (Screening) will be randomized at Visit 2 (Baseline) in a 2:2:1 ratio to one of the following three treatment arms:

- 0.1% STN1013600 ophthalmic solution BID (08:00 &  $20:00 \pm 60 \text{ min}$ )
- 0.3% STN1013600 ophthalmic solution BID (08:00 &  $20:00 \pm 60 \text{ min}$ )
- Placebo (Vehicle) BID ( $08:00 \& 20:00 \pm 60 \text{ min}$ )

Subjects will be treated for 2 months, followed by a 1-month safety follow-up without treatment (Figure 1).

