### 8.5. Exploratory Analyses

# 9. SAFETY ANALYSES

# 9.1. Safety-Related Definitions

#### 9.1.1. Adverse Event

Under Protocol 101360002IN, an AE is defined as any *on*-study untoward medical occurrence (e.g., sign, symptom, disease, syndrome, intercurrent illness) that occurs in a study subject, regardless of the suspected cause and regardless of the timing of the study medication administration. An on-study AE can occur any time after the date of informed consent through the last study visit. An AE will be considered as *treatment-emergent* if the AE occurred on or after the treatment start date up to 8 days after treatment end date (or the last study visit). Treatment-emergent AEs (TEAEs) are a subset of on-study AEs. Both on-study and TEAEs will be collected, but only TEAEs will be tabulated.

The severity of each AE will be graded by the Clinical Investigator as Mild, Moderate, or Severe. AEs will also be rated by the Investigator as to their causality/relationship to the study drug.

Each AE will be classified into a system organ class (SOC) and coded to a preferred term (PT) using Medical Dictionary for Regulatory Activities (MedDRA), version 25.1 published in September 2022.

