# 9.2. Adverse Events

Subjects with any AE(s) will be tabulated by type of AE(s) for each actual treatment received and overall. Unless otherwise specified, any AE experienced by either eye or both eyes will be counted once for that AE. In addition to the overall AE summary, subjects with any AE(s) will be tabulated by SOC and preferred term. A subject who experienced multiple AEs within a SOC or preferred term will be counted only once for that SOC or preferred term. Ocular AEs, SAEs, ADRs, Serious ADRs, non-serious AEs (including number of events) will be tabulated similarly.

AEs, AEs leading to death, AEs leading to discontinuation, SAEs, ADRs, serious ADRs, ocular AEs, and non-TEAEs, if any, will be listed separately.

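### The SAP's definition of a treatment-emergent AE has an unclear end point and omits worsening, so it can disagree with Protocol 8.3.1 on which AEs enter the by-arm tables

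*SAP*

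**What the plan says.** Protocol 8.3.1 sets the collection period: "All AEs will be collected from the signing of the Informed Consent Form (ICF) until subject withdrawal or the scheduled exit visit". The note that follows says the statistical analysis will determine and summarize treatment-emergent AEs, meaning "those AEs that began or worsened in severity after the first IP administration". It gives no closing date other than the end of collection.

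SAP 9.1.1 defines the same term differently. An AE is treatment-emergent if it occurred "on or after the treatment start date up to 8 days after treatment end date (or the last study visit"). The definition does not mention a change in severity. The section then states: "Both on-study and TEAEs will be collected, but only TEAEs will be tabulated".

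SAP 9.2 builds its incidence tables by actual treatment received. The remaining AEs appear only in listings: "AEs leading to discontinuation, SAEs, ADRs, serious ADRs, ocular AEs, and non-TEAEs, if any, will be listed separately".

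SAP 3.1 describes the last month as safety follow-up: "Subjects will be treated for 2 months, followed by a 1-month safety follow-up without treatment".

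**The concern.** The treatment-emergent flag decides which AEs, SAEs, ADRs and ocular AEs are counted by arm. If the flag has two readings, two programmers can produce different tables from the same data. On the narrower reading, most of the month that the design sets aside for safety follow-up contributes nothing to those tables.

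Visit 7 is where this matters most. SAP Tables 2 and 6 call for dilated ophthalmoscopy only at Screening and Exit, so for a completer Visit 7 holds the only scheduled post-dose dilated fundus examination. Protocol 10.3.1 treats a condition newly found after dosing as an AE. If that AE is dated at detection, around Day 90, an 8-day window excludes it from the incidence tables.

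The missing worsening clause is a separate gap, and it is present on either reading of the end point.

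**Working it through.** **End point: inputs.** Month 2 has target Day 60 and Month 3 has target Day 90 (SAP Table 4). Both visits allow ±3 days (schedule of assessments), giving Days 57–63 and 87–93. The SAP's allowance is 8 days. I assume the last dose falls on the Visit 6 day, since dosing runs through Visit 6. As a check on the timeline, 15 screening days + 90 = 105 days = 15 weeks, which agrees with the participation time in Protocol 4.1.

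**Formulas.** Window closes = last-dose day + 8. Follow-up days = exit day − last-dose day. Days outside = exit day − window close.

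| Case | Last dose | Exit | Window closes | Days outside / follow-up days | Days outside / days to exit |
|---|---|---|---|---|---|
| Target days | 60 | 90 | 68 | 22/30 = 73% | 22/90 = 24% |
| Shortest follow-up | 63 | 87 | 71 | 16/24 = 67% | 16/87 = 18% |
| Longest follow-up | 57 | 93 | 65 | 28/36 = 78% | 28/93 = 30% |

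At target days, onsets on Days 69–90 are treatment-emergent under the protocol but are not tabulated on the 8-day reading. If the bracket means through the final visit, 0 days are lost. A subject who exits the day after the last dose also loses 0 days on both readings.

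**Can the bracket be resolved from the text?** It gives no earlier-of, later-of or if-missing rule. It is not needed as a fallback for a missing last-dose date, because SAP Table 3 already handles that. If it extends the window to the final visit, the 8 days do nothing for a completer. If it means whichever comes first, the 8 days govern. The SAP does not choose.

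**Worsening: the rules side by side.**

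- Protocol 8.3.1 counts an AE that increases in severity after the first dose.
- SAP 9.1.1 counts only AEs that occurred within the window.
- Protocol 10.3.1 closes much of the gap, because it makes this an AE in its own right: "Exacerbation of a chronic or intermittent pre-existing condition including either an increase in frequency and/or intensity of the condition". A pre-existing condition that flares after dosing therefore gets a post-dose onset.
- Protocol 10.3.3, on follow-up of AEs, says: "New or updated information will be recorded in the originally completed CRF". An AE that starts between consent and first dose and then worsens can therefore keep its pre-dose onset. It is treatment-emergent under the protocol but not under the SAP.

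The group exposed is AEs starting in a screening period of up to 15 days. The documents give no AE rate, so its size cannot be derived.

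**Declared changes.** The visible text of SAP Section 10 declares a revised responder endpoint, added safety endpoints (pupil size and BCDVA) and changes to the primary analysis. It declares no change to this definition.

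**The case against.** The end-point conflict is conditional, since one reading agrees with the protocol and loses nothing. The protocol sentence is a parenthetical note about separating pre-dose from post-dose AEs, and Protocol 9 and 9.4 leave technical detail to the SAP, so a closing date could be seen as such detail. An on-treatment window is a legitimate choice, and nothing shows that 8 days is wrong in itself. The worsening gap depends on how the eCRF handles a rise in severity, which cannot be seen here. The 73% uses only off-drug days as its denominator. No safety testing is planned, every excluded AE is listed, and IOP, pupil size, BCDVA, slit-lamp and ophthalmoscopy findings are still summarized by visit through Month 3.

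Much of this stands, and it limits the size of the problem. The 24% figure belongs beside the 73%, the practical effect of the worsening gap is uncertain, and no error rate is affected. It does not remove the point. The SAP does not say which end point applies. The worsening clause is missing on both readings. A listing does not give the by-arm incidence that the safety objective's comparison with placebo needs. A sponsor may prefer an on-treatment window, but should then state it plainly and declare it as a departure from the protocol's definition.

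**Conclusion.** The concern holds. The textual mismatch is certain: the end point is ambiguous and worsening is omitted. The share of follow-up days outside the AE tables is 0% on the final-visit reading and 73% (67% to 78%) on the 8-day reading, or 24% (18% to 30%) of days from first dose to exit. These figures assume a completer whose last dose is on the Visit 6 day and who exits within the visit windows. They say nothing about how many events would be lost. The worsening gap is narrow and cannot be sized. The consequence is limited to AE incidence tables, but it should be corrected because the by-arm counts depend on an unstated choice.

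**What to change.** Rewrite the definition in SAP 9.1.1 along these lines: *a TEAE is an AE with onset, or with an increase in severity, after the first dose of study medication and up to Visit 7 or study exit.* Then:

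- Tabulate AEs, SAEs, ADRs and ocular AEs by actual treatment on that basis.
- State how a pre-dose AE that worsens is flagged when the update stays in its existing CRF record.
- If the 8-day window is kept, use it only as an additional split between on-treatment and follow-up onset.
- Declare any intended departure from Protocol 8.3.1 in SAP Section 10.

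The cost is SAP wording, a change to one derivation flag, and a data-management check on how a severity increase in a pre-dose AE can be identified. AEs are already collected through exit, so no new data are needed.

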#### 9.1.1.1. Ocular Adverse Event

An AE will be counted as an *ocular AE* if the Clinical Investigator selected "Ocular" under 'Event Location' on the AE eCRF.

#### 9.1.1.2. Adverse Drug Reaction

An AE will be counted as an *adverse drug reaction* (ADR) if the Clinical Investigator answered 'Related' to the AE eCRF question "Relationship to Study Drug."

#### 9.1.1.3. Serious Adverse Event

An AE will be counted as a *serious adverse event* (SAE) if the Clinical Investigator selected "Yes" to the question 'Is the adverse event serious?' on the AE eCRF. Any AE is considered a SAE if it fulfills one or more of the following criteria:

• Death (i.e., the AE caused or led to death)

- Life threatening (i.e., immediately life-threatening)
- It required prolonged inpatient hospitalization.
- It resulted in a persistent or significant disability/incapacity (i.e., the AE resulted in a substantial disruption of the subject's ability to carry out normal life functions).
- It resulted in a congenital anomaly/birth defect in the offspring of a study subject who was exposed to study therapy prior to conception or during pregnancy.
- It is a medically significant event(s), which may include "sight-threatening events," that may not meet any of the above serious criteria but may jeopardize the subject or require medical or surgical intervention to prevent one of the outcomes listed above.

#### 9.1.1.4. Events of Special Interest

For this study, *events of special interest* (ESI) are pregnancy and clinically significant study medication administration error.

#### 9.1.2. Safety Measures

Table 6 lists the safety measures to be evaluated for this study.

Safety Measures	Note
Intraocular pressure (IOP)	The examiner will measure IOP using a Goldmann Applanation Tonometer in each eye at least two, and sometimes three, consecutive times. IOP will be the mean of 2 readings or median of 3 readings of the first 2 readings are 3 mmHg or more apart.
Slit-lamp Biomicroscopy	Slit-lamp biomicroscopy examinations (severity scores for 12 parameters: anterior chamber cells, anterior chamber flare, lid hyperemia, lid edema, conjunctival hyperemia, conjunctival chemosis, corneal edema, corneal staining, keratic precipitates, lens, anterior synechiae of iris, posterior synechiae of iris) will be performed and graded at all visits. Cataract severity will be assessed for subjects with phakic lens.
Ophthalmoscopy	The ophthalmoscopy (fundus) examination will be performed with dilation at Visit 1 (Screening) and Visit 7 (Month 3) and without dilation at other study visits. Variables from ophthalmoscopy are cup-to-disc ratio, and assessments of vitreous, retina, macula, choroid, and optic nerve.

Table 6:Safety Assessments

Safety Measures	Note
Pupil measurement	Pupil measurement will be performed with ambient lighting conditions (10-12 lux) with an automated device. The same device should be used for all visits on a subject.
Best Corrected Distance Visual Acuity (BCDVA)	BCDVA will be recorded for right eye, left eye and both eyes at all visits using ETDRS charts. The total number of letters at 4 meters and 1 meter will be recorded. If a subject's visual acuity is so poor that he/she cannot read any chart letters when tested at 1 meter, then the subject's ability to count fingers, detect hand motion, or have light perception should be evaluated.

Table 6:	Safety	Assessments (	Continued )
	•		

The safety-related measures collected in this study include AEs, slit-lamp biomicroscopy (severity scores for 12 parameters), ophthalmoscopy (cup-to-disc ratio, and assessments of vitreous, retina, macula, choroid, and optic nerve), intraocular pressure, pupil diameter, and BCDVA. The Safety population will be used for all summaries.

All the safety-related measures will be summarized descriptively by actual treatment received. Except AEs and BCDVA, the descriptive summary of each ocular safety-related measure and the change from baseline in that measure will be performed for study eyes and fellow eyes separately.

# 9.2. Adverse Events

Subjects with any AE(s) will be tabulated by type of AE(s) for each actual treatment received and overall. Unless otherwise specified, any AE experienced by either eye or both eyes will be counted once for that AE. In addition to the overall AE summary, subjects with any AE(s) will be tabulated by SOC and preferred term. A subject who experienced multiple AEs within a SOC or preferred term will be counted only once for that SOC or preferred term. Ocular AEs, SAEs, ADRs, Serious ADRs, non-serious AEs (including number of events) will be tabulated similarly.

AEs, AEs leading to death, AEs leading to discontinuation, SAEs, ADRs, serious ADRs, ocular AEs, and non-TEAEs, if any, will be listed separately.

# 9.3. Intraocular Pressure (IOP)

IOP (mmHg) and changes from baseline will be summarized by analysis visit for study eyes and fellow eyes, separately. In addition, any worsening of  $\geq 10$  mmHg from baseline will be listed.

# 9.4. Pupil Measurement

Pupil diameter (mm) and changes from baseline will be summarized by analysis visit for study eyes and fellow eyes, separately. Any clinically significant change from baseline in pupil diameter (more than 2.5 mm) will also be listed.

# 9.5. Best Corrected Distance Visual Acuity (BCDVA)

BCVDA (ETDRS letters) and changes from baseline will be summarized by analysis visit for both eyes, study eyes, and fellow eyes, separately. In addition, any worsening of 10 letters (2 lines) or more from baseline will be listed.

## 9.6. Slit-lamp Biomicroscopy

Twelve parameters for slip-lamp biomicroscopy are (1) anterior chamber cells, (2) anterior chamber flare, (3) lid hyperemia, (4) lid edema, (5) conjunctival hyperemia, (6) conjunctival chemosis, (7) corneal edema, (8) corneal staining, (9) keratic precipitates, (10) lens (cataract), (11) anterior synechiae of iris, (12) posterior synechiae of iris. Any additional findings from biomicroscopy examination will be combined into a "Other" category for summary purpose. For each biomicroscopy parameter, frequency and percentage of rating scores will be summarized by analysis visit for study eyes and fellow eyes, separately. The rating score of "Other" category of an eye at a visit will be the most severe rating of all findings within the category. In addition, any worsening (increase) of  $\geq 2$  units from baseline in severity for all parameters except anterior chamber cells and anterior chamber flare, and any worsening from baseline in severity for anterior chamber cells and anterior chamber flare will be listed.

## 9.7. **Ophthalmoscopy**

Cup-to-disc ratio will be summarized with n, mean, standard deviation, median, minimum, and maximum by analysis visit for study eyes and fellow eyes separately. In addition, subjects with at least 0.2 increase in cup/disc ratio from baseline will be listed.

Retina, macula, choroid, vitreous, and optic nerve will be assessed as normal or abnormal. Frequency and percentage of rating will be summarized by analysis visit for study eyes and fellow eyes, separately. In addition, subjects with change from baseline from normal to abnormal in these parameters will be listed.

# **10.** SUMMARY OF CHANGES TO THE PROTOCOL

# **10.1.** Secondary and Exploratory Endpoints

#### **10.1.1.** Secondary efficacy endpoints

Based on the communication with regulatory agency, a clarification was added to the secondary efficacy endpoint "Proportion of subjects who improve 1/2/3-lines or more in Study Eye and Binocular DCNVA at each visit". The new definition of this endpoint will be "Proportion of subjects who improve 1/2/3-lines or more in Study Eye and Binocular DCNVA at each visit without loss of more than 1 line (5 letters) in Best Corrected Distance Visual Acuity (BCDVA)."

#### 10.1.2. Safety endpoints

Additional safety endpoints were added to further assess the safety of the study drug: pupil size and best corrected distance visual acuity.

